10.6.1 Objective

To determine the time to next treatment (TTNT).

10.6.2 Endpoint: Time to next treatment

Time to next treatment (TTNT) is defined as the time from the first administration of any study drug to the institution of next anti-neoplastic therapy (for any reason including disease progression, treatment toxicity and patient preference) or death due to any cause, whatever comes first.

Patients without documented institution of a new anti-neoplastic therapy will be censored at the date of last contact.

10.6.3 Analysis

- The distribution of TTNT will be estimated using the Kaplan-Meier (K-M) method. The median TTNT along with 95% confidence intervals will be presented (Brookmeyer and Crowley 1982). 25th and 75th percentiles will be considered as well.
- The TTNT probabilities at specific time points (1 month, 3 months, 6 months, 12 months, 18 months, 24 months), and the associate 95% CIs (Greenwood formula) will be summarized.
- A plot of the Kaplan-Meier curves for TTNT will be provided.
- No formal hypothesis testing will be conducted.
- The main analysis will be conducted on the FAS.

10.7 Secondary objective 7

10.7.1 Objective

To determine the safety of LEN combined with MOR00208 assessed according to the frequency and severity of adverse events (AEs).

10.7.2 Endpoint: Incidence, frequency and severity of treatment-emergent adverse events (AEs)

10.7.3 Analysis

With the exception of the Listing on pre-treatment AEs emerging in patients who have never been exposed to any drug, all safety analyses including the analysis on AEs will be conducted using the Safety Set (SAF). The pre-treatment AEs emerging in patients who have never been exposed to any drug will be reported on the population of “All screened patients”.

20.1.1 Overview

The analysis of safety assessments in this trial will include summaries of the following categories of safety and tolerability:

1. Adverse Events (AEs, number and severity)
 - Treatment-emergent AEs (TEAEs)
 - Treatment-emergent Serious AEs (SAEs)
 - TEAEs by maximum toxicity grade
 - TEAEs by intensity
 - TEAE suspected to be related to a study drug
 - TEAEs leading to study discontinuation and AEs leading to death
 - AEs of special interest (AESI)
2. Vital signs: systolic blood pressure (SBP), diastolic blood pressure (DBP) and heart rate
3. Physical Examination
4. 12-lead ECG parameters: PR, QRS, RR and QT interval values
5. Laboratory safety evaluations (blood chemistry, haematology, coagulation, urinalysis, anti-MOR00208 antibodies)
6. ECOG Performance Status
7. B-Symptoms

21.1.1 Adverse events

An AE is defined as any untoward medical occurrence in a patient or participant in a clinical trial administered a medicinal product, which does not necessarily have a causal relationship to this treatment.

**STATISTICAL ANALYSIS PLAN**MorphoSys AG
MOR208C203

An AE can therefore be any unfavourable and unintended sign (including an abnormal laboratory finding), symptom, or disease temporally associated with the use of a study drug, whether or not it is considered related to that study drug. AEs include any clinically significant deterioration of a patient's medical status after the signing of the informed consent form (ICF). Also, an increase in the frequency or intensity of a pre-existing event or conditions and events resulting from protocol mandated procedures (e.g., invasive procedures) fall under the definition of AEs.

In addition, overdoses exceeding the planned infusion dose by 20% should be recorded as AEs.

Please note that in the context of this protocol symptoms that are clearly associated to the progression of underlying malignancy (DLBCL) do not fall under the definition of AEs.

Each AE will be reported to determine the following:

- Relationship to the study drug(s) (suspected/not-suspected)
- Duration (start and end date, or if continuing at end of study)
- NCI-CTCAE Grade (see below)
- Intensity: the intensity of all AEs will be graded as mild, moderate, or severe using the following definitions:
 - mild: tolerable
 - moderate: interferes with normal activity
 - severe: incapacitating (causes inability to perform usual activities or work)
- Outcome
- Action taken with study drug(s)
 - no action taken
 - study drug temporarily interrupted
 - study drug permanently discontinued due to this AE
- Other action taken (medication taken; non-drug therapy given; hospitalisation/ prolonged hospitalisation)
- Seriousness: whether it is serious, where an SAE is defined as one that:
 - results in death
 - is life-threatening
 - requires inpatient hospitalisation or prolongation of existing hospitalisation (hospitalisation signifies that the patient was an inpatient for at least one overnight stay) unless hospitalisation is for:
 - Routine treatment or monitoring of the studied indication, not associated with deterioration of symptoms related to DLBCL.

-
- Elective or pre-planned treatment for a pre-existing condition that is unrelated to DLBCL and has not worsened since signing of the ICF.
 - Social reason and respite care in the absence of any deterioration in the patient's general condition.
 - Results in persistent or significant disability or incapacity.
 - Is a congenital anomaly or birth defect.
 - Is medically significant, i.e., defined as an event that jeopardizes the patient or may require medical intervention to prevent one of the outcomes listed previously.

22.1.1 Treatment-emergent adverse events

An **on-treatment adverse event (or Treatment-emergent Adverse Event – TEAE)** is defined as any adverse event reported in the following time interval (including the lower and upper limits): date of first administration of any study drug; date of last administration of any study drug + 30 days.

If the last date of study drug administration is missing, on-treatment assessments/events include any assessment/event recorded in the database and which occur after the start date of study treatment. Safety summary tables including summaries of on-treatment deaths will be based only on on-treatment assessments/events.

An adverse event present prior to study drug administration but increased in severity after treatment start, will also be included as TEAE.

Events with missing onset dates will be included as TEAE if the end date is not before the start date of treatment.

Adverse events occurring or worsening later than 30 days after the date of last study drug administration or the date of completion/discontinuation of the study are defined as TEAE if these are considered to be related to the study drug.

If the start date and time of an AE are partially or completely missing, the AE will be assumed to be a TEAE if it cannot be definitely shown that the AE did not occur or worsen during the treatment-emergent period (worst case approach). Missing dates and times will not be replaced.

Thus, the following approach will be taken:

- If the start time of an AE is missing but the start date is complete, an AE will only be excluded from TEAE if start day is before day of first treatment or start day is after end day of treatment-emergent period.
- If start time and day are missing but the start month is complete, an AE will only be excluded from TEAE if start month is before month of first treatment or start month is

-
- after end month of treatment-emergent period or if stop date/time is before start of first treatment.
- If start day and months are missing but the start year is complete, an AE will only be excluded from TEAE if start year is before year of first treatment or if start year is after end year of treatment-emergent period or if stop date/time is before start of first treatment.
 - If start date is completely missing, an AE will not be excluded from TEAE unless the stop date/time is before start of first treatment.

If the last date of study treatment is missing, on-treatment assessments/events include any assessment/event recorded in the database and which occur after the start date of study treatment.

The incidence of treatment-emergent AEs will be summarized in incidence tables. If a patient experiences more than one occurrence of the same AE, the occurrence with the greatest severity and the closest association with the study drug will be counted in the summary tables. All AEs will be listed by patient, along with information regarding onset, duration, relationship to study drug, intensity, toxicity grade, action taken with study drug, treatment of event, and outcomes.

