10.7.3.1.2 AE listings

- i. All AEs will be listed by patient, along with information regarding onset, duration, relationship to study drugs, intensity, toxicity grade, action taken with study drug, treatment of event, and outcomes. This listing will be generated for all patients in the SAF.
- ii. In the AE listings, AEs that started prior to the administration of any study drug will be flagged as pre-treatment AEs. AEs that start 30 days after the last study treatment and which are not related to one of the study drugs will be flagged as post-treatment AEs.
- iii. Special AE listings displaying details of the event(s) captured on the eCRF in a compact format will be provided for:
 - Serious Adverse Events.
 - TEAEs of toxicity grade 3 or grade 4.
 - AEs leading to discontinuation of treatment (split by MOR00208, LEN and overall).
 - TEAEs of special interest.
 - TEAEs suspected to be related to study drug

-
- Treatment-emergent SAEs
 - TEAEs pertaining to the SOC '*infections and infestations*'
 - AEs leading to death.
 - Pre-treatment adverse events (i.e., adverse events that happened before administration of any study drug). This listing will be generated for all patients successfully screened but never treated. The pre-treatment AEs will be determined using the analysis population of 'All screened patients'.

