10.7.3.1.5 AESIs

AEs of special interest will be presented by primary SOC, PT and grade.

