10.7.3.1.7 Overall Summary of AEs

In addition, an **Overall AE summary table** will be presented showing the incidence and number of patients with at least one of the events:

- At least one TEAE.
- At least one treatment-emergent SAE.
- On-treatment deaths.
- Post-treatment deaths.
- At least one treatment-emergent SAE suspected to be related to the study drug (split by MOR00208, LEN, MOR00208 and LEN, and any study drug).
- At least one TEAE suspected to be related to the study drug (split by MOR00208, LEN, MOR00208 and LEN, and any study drug).
- At least one drug-related TEAE with grade 3 or grade 4 (split by MOR00208, LEN, MOR00208 and LEN, and overall).
- At least one drug-related TEAE by intensity (split by MOR00208, LEN, MOR00208 and LEN, and overall).
- At least one AESI.
- At least one TEAE leading to any action on MOR00208, on LEN, on MOR00208 and LEN, or on any study drug
- TEAEs leading to discontinuation of treatment (split by MOR00208, LEN, MOR00208 and LEN, and overall).
- Treatment-emergent SAEs of grade 5.
- At least one TEAE of PT 'Infusion-related reactions (IRRs)' \geq grade 3

Additional safety-related analyses on vital signs, physical examinations, electrocardiogram, and laboratory data are being described in Section 13.

10.8 Secondary objective 8

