16.5 Subgroup analyses

16.5.1 Patients who discontinued LEN treatment

Efficacy assessment

A Kaplan-Meier analysis on PFS and OS will be conducted as described in Sections 10.2 and 10.4 for those patients who discontinued LEN treatment at any point in time. That is, regardless whether the discontinuation is due to an adverse event, or as per protocol after Cycle 12. The analysis will start from the moment of LEN discontinuation (zero time elapsed). Both Tables and Kaplan-Meier curves will be produced based on the FAS.

Safety assessment

Incidence and frequency of adverse events will be displayed separately for the periods *before* LEN discontinuation, and *after* LEN discontinuation. All discontinuations of LEN treatment are considered, regardless of the reason for discontinuation (per protocol, or due to AE).

TEAEs are considered for the **pre**-LEN discontinuation period if they are observed in the following interval (including the lower and upper limits): date of first administration of study treatment to date of last administration of LEN + 7 days (or if they are suspected to be related to LEN).

TEAEs are considered for the **post**-LEN discontinuation period if they are observed in the following interval (including the lower and upper limits): date of last administration of LEN + 8 days to date of last administration of MOR00208 + 30 days (if they are not suspected to be related to LEN).

For both periods following will be summarized by SOC, PT, and NCI-CTCAE Grade for the SAF:

- All TEAEs
- TEAEs by ,Search Category' (see Section 16.3.1)
- SAEs
- AESIs
- G3 vs. G4 TEAEs

Moreover, a Table summarizing fatal TEAEs (i.e., Grade 5 SAEs) will be produced.

A barplot will be produced illustrating the TEAEs that happened with an incidence of $\geq 10\%$ of patients in the SAF. Each bar will represent a particular PT, and for each bar the fraction of patients with Grade 1, 2, 3, 4, 5 will be indicated by color-coding or shading.

Exposure as described in Section 8.9.2 will be calculated for both the **pre**-LEN discontinuation period (exposure to LEN or the combination LEN/MOR00208), and the **post**-LEN discontinuation period (exposure to MOR00208). The exposure to LEN or the combination for the **pre**-LEN discontinuation period is starting from the first date of LEN dosing. The exposure to MOR00208 only for the **post**-LEN discontinuation period is starting from the first administration of MOR00208 after the discontinuation of LEN.

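### Second primary malignancies that arise late and are rated not suspected fall outside the AESI listing and, on the natural reading, the AESI summary tables, although the protocol collects them for years regardless of causality

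*SAP*

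**What the plan says.** **Definition.** SAP section 22.1.1 (Treatment-emergent adverse events, within 10.7.3) runs the treatment-emergent window from first dose to last dose plus 30 days. Events beginning or worsening more than 30 days after the last dose "or the date of completion/discontinuation of the study are defined as TEAE if these are considered to be related to the study drug". The same section sets a general rule: "Safety summary tables including summaries of on-treatment deaths will be based only on on-treatment assessments/events".

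**Outputs that name AESIs.** The SAP counts SPM as an AESI.
- Section 10.7.3.1.2 plans a special listing of "TEAEs of special interest".
- Section 10.7.3.1.5 says "AEs of special interest will be presented by primary SOC, PT and grade" and gives no period.
- Section 10.7.3.1.7 has a row "At least one AESI", also without a period.

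**Other listings.** Section 10.7.3.1.2 also lists all adverse events, where "AEs that start 30 days after the last study treatment and which are not related to one of the study drugs will be flagged" (the flag marks them post-treatment). It plans a listing of serious adverse events, separate from the treatment-emergent one, and a listing of adverse events leading to death. Section 14.5 adds that all collected data will be shown in patient listings.

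**Protocol.** Section 7.2.12 makes every SPM a reportable serious adverse event whatever its causality, from Cycle 1 Day 1 through a follow-up of up to 3 years. Table 5 (footnote 9) and section 7.2.5 have the site ask about SPMs every 90 days; the footnote says for at least 5 years from Cycle 1 Day 1, section 7.2.5 up to 5 years.

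**The concern.** A second cancer is a delayed harm, and the protocol treats it as one. Under protocol 8.2, ordinary adverse events are recorded after the 30-day visit only if they are judged related. SPMs are exempt: in Table 5 the adverse event row stops at the 30-day visit, while the SPM row continues into survival follow-up. The SAP then applies the ordinary filter of 30 days or relatedness to the outputs that carry SPMs by name.

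At stake is the SPM count that a reader takes from the summary tables. Under the filter, that count covers treatment plus 30 days and, after that, only cases that the investigator attributes to study drug. In a single-arm trial, attribution of a late second cancer is a judgement without a comparator, so it is a weak basis for deciding which cases are counted.

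**Working it through.** The plan states no figure on this point, so there is nothing to reproduce. The check follows one case through the planned outputs: an SPM starting more than 30 days after the last dose and rated not suspected.

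1. **Treatment-emergent status.** It is outside the 30-day window and not related, so it is not a TEAE. An SPM with no causality rating counts as related (SAP 24.1.1, Relationship to study drug) and stays a TEAE. So does one rated suspected. Only an explicit rating of not suspected is affected.
2. **AESI listing.** It is restricted to TEAEs, so the case is out.
3. **AESI table and AESI row.** Neither states a period, so the general rule in 22.1.1 applies. That section equates on-treatment adverse events with TEAEs, and SAP 6.8 also ends the on-treatment period at last dose plus 30 days. On either definition the case is out. Where the SAP sets a period for AESIs elsewhere, it is bounded in the same way. Section 16.5.1 uses "date of last administration of LEN + 8 days to date of last administration of MOR00208 + 30 days" for the later period, and 16.5.3 places AESIs under an incidence-of-TEAEs heading.
4. **Listings.** The case is in the all-event listing, flagged post-treatment, and in the serious adverse event listing. If fatal, it is in the listing of events leading to death.
5. **Death summaries (10.7.3.1.6).** A fatal case is counted, but grouped only by relation to disease progression and not identified as an SPM.

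**Scale of the time involved (illustration only).** Treatment duration is assumed, and the collection period is measured from Cycle 1 Day 1.

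Share of the period beyond last dose + 30 days = 1 − (28 × cycles + 30) / days in period.

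| Cycles | Window (days) | 5 years (1826 days) | 3 years (1096 days) |
|---|---|---|---|
| 6 | 198 | 1 − 198/1826 = 89% | 1 − 198/1096 = 82% |
| 12 | 366 | 1 − 366/1826 = 80% | 1 − 366/1096 = 67% |
| 24 | 702 | 1 − 702/1826 = 62% | 1 − 702/1096 = 36% |

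These shares are for a patient observed to the end. Death and loss reduce them. A pooled version uses exponential times with the medians that protocol 1.3.3 quotes for lenalidomide plus rituximab (PFS 3.7 months, OS 10.7 months). Here H is the horizon, L the time to loss to follow-up, and x the extra months of treatment after progression:

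share = (E[min(OS, L, H)] − E[min(PFS, L, H)] − x − 1) / E[min(OS, L, H)]

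- No loss, x = 0. H = 36: (13.94 − 5.33 − 1)/13.94 = 55%. H = 60: (15.12 − 5.34 − 1)/15.12 = 58%.
- 10% lost per year, x = 3. H = 36: (12.63 − 5.09 − 3 − 1)/12.63 = 28%. H = 60: (13.43 − 5.10 − 3 − 1)/13.43 = 32%.

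These are shares of follow-up time, not of SPMs. They borrow from another regimen and are not bounds for this trial.

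**The case against.** **The AESI table may cover all periods.** Section 10.7.3.1.5 speaks of AEs where its neighbours say treatment-emergent, the SAP says AESIs are monitored continuously, and the overall summary has a row for "Post-treatment deaths". This reading is possible, so exclusion from the table is an inference, though the better supported one. If the all-period reading is right, the AESI table and the AESI listing would disagree. A clarifying sentence is needed either way.

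**The SAP gives the AESI table no period at all.** A reader might infer this from 10.7.3.1.5 and 10.7.3.1.7 alone. The documents do not support it: the rule in 22.1.1 supplies a default, and only those two sections are silent.

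**The exposure-adjusted rates are wrong too.** A reader might infer this because sections 20.11.3 and 23.1.1 of Addendum 8.0 count TEAEs only. Their denominator is time on drug. Adding unrelated events from years off drug would mismatch numerator and denominator, so these rates are not at fault. A rate over total follow-up is a separate analysis.

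**Late SPMs are lost from the report.** They are not. The listings named above show them, and 14.5 covers all collected data. Section 14.5 allows either listing or tabulation, however, so it does not guarantee a count.

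**A late unrelated SPM is hard to interpret.** In about 80 patients without a control arm, and with later therapies as a competing cause, this is fair. It argues for flagging such cases, not for leaving them out of the count.

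**Conclusion.** The point holds as a gap in planned presentation. Followed as written, the SAP leaves late SPMs rated not suspected out of the AESI listing and, most naturally, out of the AESI table and the AESI row. No planned table clearly counts SPMs over the follow-up that the protocol requires.

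The exclusion from the listing is explicit. The exclusion from the table and row rests on applying the general rule in 22.1.1 to sections that state no period of their own. The number of cases affected cannot be estimated from the documents; it could be zero. No efficacy result and no other safety result depends on it. It is a cheap improvement that should be made, because it can change the reported count of a delayed harm that the protocol singled out.

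**What to change.** In SAP 10.7.3.1.5:
- Summarise SPMs on the safety set from first dose to death or last contact, regardless of causality and of time since last dose.
- Give number (%) and rate per patient-year of total follow-up, split into on-treatment and post-treatment.
- Flag SPMs that arise after the start of subsequent antineoplastic therapy.
- State the period used for the AESI table and for the AESI row in 10.7.3.1.7.

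In SAP 10.7.3.1.2, include all SPMs in the AESI listing, not only treatment-emergent ones.

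The cost is a short SAP addition and one extra table from data already collected. The reported SPM count may rise, and late cases will be partly confounded by later therapy, which the flag makes visible.

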23.1.1 Adverse events of special interest

Adverse events of special interest (AESI) are:

- Tumour flare (TFR)
- Tumour lysis syndrome (TLS),
- Second primary malignancy (SPM)
- Infusion-related reactions (IRRs) \geq grade 3
- Allergic reactions to study drug \geq grade 3
- Cytokine release syndrome
- Overdoses

Unlike routine safety assessments, SAEs and AESI are monitored continuously and have special reporting requirements.

24.1.1 Relationship to study drug

The Investigator should determine the causality (relationship to the study drug) based on his/her clinical experience, on Summary of Product Characteristics (SmPC) and Prescribing Information, and on the information given in the Investigator's Brochure (IB) for MOR00208 and the SmPC/prescribing information for LEN. The causal relationship of all AEs to the study drug will be judged as either suspected or not suspected. A suspected causal

relationship means at least a reasonable possibility that the event is caused by the study drug. If no relationship has been provided by the Investigator, the event will be considered as related to the study drug.

25.1.1 Coding of adverse events

Adverse events will be coded according to the Medical Dictionary for Regulatory Activities (MedDRA) and will be reported by primary system organ class (SOC) and preferred term (PT). The MedDRA version used for reporting the study will be the version used for coding the trial and will be specified in the clinical study report and as a footnote in the related outputs (if possible).

26.1.1 Grading of adverse events

Toxicity grade: determined according to the National Cancer Institute- Common Terminology Criteria for Adverse Events (NCI-CTCAE) version 4.03 of June 14, 2010 (or higher), using the following definitions:

- Grade 1: mild; asymptomatic or mild symptoms; clinical or diagnostic observations only; intervention not indicated
- Grade 2: moderate; minimal, local or noninvasive intervention indicated; limiting age-appropriate instrumental activities of daily living (refers to preparing meals, shopping for groceries or clothes, using the telephone, managing money, etc.)
- Grade 3: severe or medically significant but not immediately life-threatening; hospitalisation or prolongation of hospitalisation indicated; disabling; limiting self-care activities of daily living
- Grade 4: life-threatening consequences; urgent intervention indicated
- Grade 5: death related to AE

The CTCAE represents a comprehensive grading system for reporting the acute and late effects of cancer treatments. CTCAE grading is by definition a 5-point scale generally corresponding to mild, moderate, severe, life threatening, and death. This grading system inherently places a value on the importance of an event although there is not necessarily proportionality among grades (a grade 2 is not twice as bad as a grade 1).

